6. DOSING DELAYS/DOSE MODIFICATIONS

No dose modifications are allowed in this protocol. Nivolumab can be ‘continued’, ‘delayed’, ‘withheld’ or ‘permanently discontinued’.

See Appendix C to the protocol for toxicity management algorithms which include specific treatment guidelines. These algorithms should be followed unless there are specific clinical circumstances which the treating physician indicates variations or alternative treatment is needed.

6.1 Guideline for Nivolumab Related Adverse Events in General

ALL NON-IMMUNOLOGIC EVENTS*	Management/Next Dose for Nivolumab
≤ Grade 1	No change in dose
Grade 2	Hold until ≤ Grade 1 OR baseline Resume at same dose level.
Grade 3	Hold* until ≤ Grade 1 continue at investigator discretion
Grade 4	Off protocol therapy
* Not agent related, OR agent-related but non-immunologically mediated	
Recommended management: As clinically indicated	
ALL IMMUNOLOGIC EVENTS	Management/Next Dose for Nivolumab
≤ Grade 1	No change in dose
Grade 2	Hold until ≤ Grade 1 OR baseline* When resolved < or following steroids resume at same dose level.
Grade 3	Off protocol therapy (exceptions noted in 5.3)
Grade 4	Off protocol therapy
Recommended management: As clinically indicated	

6.2 Guideline for Specific Nivolumab Related Adverse Events

Skin Rash and Oral Lesions	Management/Next Dose for Nivolumab
≤ Grade 1	No change in dose *
Grade 2	Hold* until ≤ 1 Grade resolved. Consider steroid treatment if > 7 days. Resume at same dose level.
Grade 3	Hold* until ≤ Grade 1. Consider steroid treatment. Resume at same level at investigator discretion
Grade 4	Off protocol therapy
*Patients with purpuric or bullous lesions must be evaluated for vasculitis, Steven-Johnson syndrome, TEN, and autoimmune bullous disease including oral lesions of bullous pemphigus/pemphigoid. Pruritus may occur with or without skin rash and should be treated symptomatically if there is no associated liver or GI toxicity. Note skin rash typically occurs early and may be followed by additional events particularly during steroids tapering.	
Recommended management: AE management guidelines	

Liver Function: ALT, AST, total bilirubin	Management/Next Dose for Nivolumab
≤ Grade 1	Continue nivolumab and monitor liver enzymes as per protocol.
Grade 2	Hold until ULN or baseline. Resume at same dose level. Consider steroid treatment > 7 days
Grade 3	Off protocol therapy
Grade 4	Off protocol therapy
Continuation of nivolumab during active immune-mediated hepatitis may exacerbate the inflammation. Holding drug to evaluate LFT changes and early treatment are recommended. LFT changes may occur during steroid tapers from other events and may occur together with other GI events including cholecystitis /pancreatitis.	
Recommended management: see Hepatic AE management algorithm (Appendix C)	

Diarrhea/ Colitis	Management/Next Dose for Nivolumab
≤ Grade 1	Hold until Grade 0 or baseline. No change in dose
Grade 2	Hold until Grade 0 or baseline. Consider steroid treatment if lasting > 7 days, if condition does not improve within a reasonable time frame, the patient should be withdrawn from study if this is in the best interest of the patient as judged by the investigator.
Grade 3	Off protocol therapy.
Grade 4	Off protocol therapy
See GI AE Algorithm for management of symptomatic colitis. Patients with grade 2 symptoms but normal colonoscopy and biopsies may be retreated after resolution. Please evaluate pituitary function prior to starting steroids if possible without compromising acute care. Evaluation for all patients for additional causes includes C. diff, acute and self-limited infectious and foodborne illness, ischemic bowel, diverticulitis, and inflammatory bowel disease.	
Recommended management: see GI AE management Algorithm (Appendix C)	

Pancreatitis Amylase/Lipase*	Management/Next Dose for Nivolumab
≤ Grade 1	Hold dose until grade 0
Grade 2	Hold until Grade 0. Resume at same dose level if asymptomatic
Grade 3**	Hold until Grade 0. Resume at same dose level if asymptomatic. Patients who develop symptomatic pancreatitis or diabetes mellitus should be taken off treatment
Grade 4**	Patients who develop symptomatic pancreatitis or diabetes mellitus should be taken off treatment
Patients may develop symptomatic and radiologic evidence of pancreatitis as well as diabetes mellitus and diabetic ketoacidosis. Lipase elevation may occur during the period of steroid withdrawal and with other immune mediated events or associated with colitis, hepatitis, and patients who have asymptomatic lipase elevation typically have self-limited course and may be retreated. For treatment management of symptomatic pancreatitis please follow the Hepatic Adverse Event Management Algorithm (Appendix C). * In sites where lipase analysis is not readily available, monitoring with amylase level will suffice. **Grade 3 or 4 amylase or lipase abnormalities that are not associated with diabetes mellitus (DM), associated liver or gall bladder inflammation clinical manifestations of pancreatitis and which decrease to Grade 0 may resume study treatment when resolved.	

Pneumonitis	Management/Next Dose for Nivolumab
≤ Grade 1	Hold dose pending evaluation and resolution to ≤ Grade 0 or baseline. Resume no change in dose. Consultation with pulmonary and/or infectious disease (ID) specialist is recommended.
Grade 2	Hold dose pending evaluation. Resume no change in dose after pulmonary and/or ID consultation if lymphocytic pneumonitis is excluded. Off study if steroids are required.
Grade 3	Off protocol therapy
Grade 4	Off protocol therapy
Distinguishing inflammatory pneumonitis is often a diagnosis of exclusion for patients who do not respond to antibiotics and have no causal organism identified including influenza. Most patients with respiratory failure or hypoxia will be treated with steroids. Bronchoscopy may be required and analysis of lavage fluid for lymphocytic predominance may be helpful. Patients with new lung nodules should be evaluated for sarcoid like granuloma. Please consider recommending seasonal influenza killed vaccine for all patients.	
Recommended management: See Pulmonary Adverse Event Management Algorithm (Appendix C)	

Other GI, Nausea-Vomiting	Management/Next Dose for Nivolumab
≤ Grade 1	No change in dose.
Grade 2	Hold until ≤ Grade 1. Resume at same dose level after resolution to ≤ Grade 1. If recurs after resuming nivolumab, evaluate for gastritis duodenitis and other immune adverse events or other causes
Grade 3	Hold pending evaluation until ≤ Grade 1. Evaluate for gastritis duodenitis and other immune adverse events or other causes. Resume at same dose level. If symptoms do not resolve within 7 days with symptomatic treatment patients should go off protocol therapy
Grade 4	Off protocol therapy
Patients with grade 3 (or recurrent grade 2) nausea-vomiting should be evaluated for upper GI inflammation and other immune related events.	

Fatigue	Management/Next Dose for Nivolumab
≤ Grade 1	No change in dose.
Grade 2	No change in dose
Grade 3	Hold until ≤ Grade 2. Resume at same dose level
Grade 4	Off protocol therapy
Fatigue is the most common adverse event associated with immune checkpoint therapy. Grade 2 or greater fatigue should be evaluated for associated or underlying organ involvement including pituitary, thyroid, and hepatic, or muscle (CPK) inflammation	

Neurologic events	Management/Next Dose for Nivolumab
≤ Grade 1	Hold dose pending evaluation and observation. Resume with no change in dose.*
Grade 2	Hold dose pending evaluation and observation. Hold until ≤ Grade 1.* Off protocol therapy if treatment with steroids is required. Resume at same dose level for peripheral isolated n. VII (Bell's palsy).
Grade 3	Off protocol therapy
Grade 4	Off protocol therapy
*Patients with any CNS events including aseptic meningitis, encephalitis, symptomatic hypophysitis, or myopathy, peripheral demyelinating neuropathy, cranial neuropathy (other than peripheral n. VII), Guillain Barre syndrome, myasthenia gravis should be off study.	
Recommended management: See Neurologic Adverse Event Management Algorithm (Appendix C)	

Endocrine Hypophysitis Adrenal Insufficiency	Management/Next Dose for Nivolumab
≤ Grade 1	Asymptomatic TSH elevation * Hold pending evaluation, consider endocrine consultation.
Grade 2	Hold until patients are on a stable replacement hormone regimen. If treated with steroids patients must be stable off steroids for two weeks. Resume at same dose level.
Grade 3	Off study treatment.
Grade 4	Off protocol therapy
Note all patients with symptomatic pituitary enlargement, exclusive of hormone deficiency, but including severe headache or enlarged pituitary on MRI should be considered grade 3 events. Isolated thyroid or testosterone deficiency may be treated as grade 2 if there are no other associated deficiencies and adrenal function is monitored. Please evaluate pituitary function before beginning steroid therapy or replacement therapy of any kind.	
*Note patients with thyroiditis may be retreated on replacement therapy. Patients must be evaluated to rule out pituitary disease prior to initiating thyroid replacement.	
Recommended management: See Endocrine Management Algorithm (Appendix C)	

Fever	Management/Next Dose for Nivolumab
≤ Grade 1	Hold dose pending evaluation and observation. Resume with no change in dose if patient is clinically stable*.
Grade 2	Hold until ≤ Grade 1. Resume at same dose level.
Grade 3	Hold until ≤ Grade 1. Resume at same dose level.
Grade 4	Off treatment
*Patients with fever should be evaluated as clinically appropriate. Patients may experience isolated fever during infusion reactions or up to several days after infusion. Evaluation over the course of 1-2 weeks should be done for other autoimmune events that may present as fever	
See section 5.6 for management of infusion reactions	

Cardiac *	Management/Next Dose for BMS-936558 (Nivolumab) + Ipilimumab Cardiac Toxicities
≤ Grade 1	Hold dose pending evaluation and observation.** Evaluate for signs and symptoms of CHF, ischemia, arrhythmia or myositis. Obtain history EKG, CK (for concomitant myositis), CK-MB. Repeat troponin, CK and EKG 2-3 days. If troponin and labs normalize may resume therapy. If labs worsen or symptoms develop then treat as below. Hold pending evaluation
Grade ≥2 with suspected myocarditis	Hold dose.** Admit to hospital. Cardiology consult. Rule out MI and other causes of cardiac disease. Cardiac Monitoring. Cardiac Echo. Consider cardiac MRI and cardiac biopsy. Initiate high dose methylprednisolone. If no improvement within 24 hours, add either infliximab, ATG or tacrolimus. Consult algorithm for more details. Resume therapy if there is a return to baseline and myocarditis is excluded or considered unlikely.
Grade ≥2 with confirmed myocarditis	Off protocol therapy. Admit to CCU (consider transfer to nearest Cardiac Transplant Unit). Treat as above. Consider high dose methylprednisolone Add ATG or tacrolimus if no improvement. Off treatment.

*Including CHF, LV systolic dysfunction, Myocarditis, CPK, and troponin
 
**Patients with evidence of myositis without myocarditis may be treated according as “other event”
 
Note: The optimal treatment regimen for immune mediated myocarditis has not been established. Since this toxicity has caused patient deaths, an aggressive approach is recommended.
	

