5.5.2 Restarting Nivolumab in Patients Treated with Corticosteroids

Grade 2 events must resolve to \leq Grade 1 before considering retreatment.

All patients treated with steroids for grade 2 events should have nivolumab withheld until resolution to \leq Grade 1 for at least 2 weeks following complete removal from steroid treatment except for maintenance replacement doses for adrenal insufficiency (preferably no greater than 10mg prednisone equivalent daily).

All patients treated with steroids for grade ≥ 3 events should have nivolumab discontinued.

Patients with grade 3 thyroiditis and skin rash may continue therapy, as for grade 2 events with resolution and stable replacement treatment.

Patients with hepatitis, pancreatitis, pneumonitis, and colitis are at risk for exacerbation with retreatment if there is residual inflammation and should resolve to Grade 0 or baseline before retreatment. Baseline can mean the initial grade i.e. grade <1 where permitted on study.

Patients with thyroiditis or hypopituitarism who are stable as above may be restarted with replacement hormones including thyroid hormone and physiologic doses only of corticosteroids. Please note that grading and for hypophysitis with symptoms of headache, visual or neurologic changes or radiologic evidence of pituitary enlargement and other CNS events such as aseptic meningitis or encephalitis should be considered grade 3 events.

New immune related events or exacerbation of existing events during steroid treatment or taper suggest the presence of ongoing immune activation and should require permanent discontinuation of nivolumab.

A patient who is treated with steroids, evaluated, and found to not have an autoimmune or inflammatory event requiring steroid treatment, may be restarted if asymptomatic off steroids for 2 weeks and other restarting criteria are met.

Prior to starting corticosteroids or hormone replacement for any reason, appropriate endocrine testing including cortisol, ACTH, TSH and T4 must be drawn if clinically feasible to document baseline function and distinguish the pituitary from peripheral organ dysfunction and later from steroid (or thyroid) treatment associated ACTH (or TSH) suppression. Steroids should be started prior to obtaining results based on clinical indications.

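### The restart rules in 5.5.2 and 6.1 make no exception for the grade 2 pneumonitis and neurologic events that 6.2 stops when steroids are required

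*Combined protocol and SAP*

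**What the plan says.** Section 6.2, pneumonitis, grade 2: the dose is held pending evaluation. The row then reads "Resume no change in dose after pulmonary and/or ID consultation if lymphocytic pneumonitis is excluded", followed by "Off study if steroids are required". Section 6.2, neurologic events, grade 2: the dose is held, and protocol therapy ends if steroids are needed. A footnote to that table also takes a list of diagnoses off study: CNS events, myopathy, peripheral demyelinating neuropathy, cranial neuropathy other than nerve VII, Guillain-Barré syndrome and myasthenia gravis.

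Section 5.5.2 deals with restarting after corticosteroids. Its general rule begins "All patients treated with steroids for grade 2 events should have nivolumab withheld until resolution" to Grade 1 or lower, for at least 2 weeks after steroids have been fully stopped. It continues: "Patients with hepatitis, pancreatitis, pneumonitis, and colitis are at risk for exacerbation with retreatment if there is residual inflammation", and says these events "should resolve to Grade 0 or baseline before retreatment". On the nervous system it says only that hypophysitis with symptoms or pituitary enlargement and "other CNS events such as aseptic meningitis or encephalitis should be considered grade 3 events".

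Section 6.1, immunologic events, grade 2: hold, then "following steroids resume at same dose level". The only exceptions that this table refers to are the grade 3 ones in 5.3.

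**The concern.** Two sections that a site would consult about the same patient point in different directions. A patient whose grade 2 pneumonitis needed steroids, and who has fully recovered off them, meets every condition that 5.5.2 sets. The general row in 6.1 also says to resume. The pneumonitis row in 6.2 says the patient is finished with nivolumab.

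What is at stake is re-exposure of a patient whom the event-specific table meant to stop. Section 2.2.6 reports pulmonary toxicity resulting in 3 deaths, and 13.4.1 lists pneumonitis among the events to be captured and followed over time. There is also a conduct question: in a multicenter trial, neither a site nor a monitor can tell from the text whether a restart under 5.5.2 would be a protocol deviation.

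**Working it through.** No published figure is being tested, so the check sets the rules side by side for the kinds of patient they could cover. In each case the patient has been off steroids for 2 weeks.

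| Patient | 5.5.2 | 6.2 | Agree? |
|---|---|---|---|
| Grade 2 pneumonitis that required steroids, now Grade 0 | Restart conditions met | Stopped | No |
| Grade 2 non-CNS neurologic event that required steroids, not in the footnote, now Grade 1 or lower | Restart conditions met | Stopped by the row | No |
| Grade 2 Guillain-Barré syndrome, myasthenia gravis or another non-CNS footnote diagnosis that required steroids, now Grade 1 or lower | Restart conditions met; diagnosis not mentioned | Stopped by row and by footnote | No, but 6.2 says it twice |
| CNS event such as aseptic meningitis | Counted as grade 3, so discontinued | Stopped by footnote | Yes |
| Isolated nerve VII palsy treated with steroids | Restart conditions met | Unclear: the row stops steroid-treated events, then allows resumption for this palsy | Cannot be settled from the text |
| Started on steroids, then found not to need them | May restart | Steroids were not required, so the stop does not apply | Yes |

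**Which patients does the pneumonitis sentence in 5.5.2 reach?** The section concerns steroid-treated patients. It discontinues those treated for grade 3 or higher, apart from thyroiditis and skin rash, and the grade 1 pneumonitis row in 6.2 does not call for steroids. What remains is mainly grade 2 pneumonitis treated with steroids, which is the group 6.2 stops.

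**Does another section settle it?** Section 5.5.1 treats grade 2 events as a class that may restart. Section 5.5.2 does the same when it says "Patients with grade 3 thyroiditis and skin rash may continue therapy, as for grade 2 events with resolution and stable replacement treatment". Section 5.3 stops grade 3 pneumonitis and neurologic events, and any patient needing immunosuppression beyond steroids, but lists neither grade 2 stop. Section 5.1 sends dose decisions to section 6, and 5.3 also points there; both favor 6.2 without saying that it overrides 5.5.2. The Appendix C algorithms are figures not reproduced in the text, so they can be counted neither for nor against.

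**How many patients?** The documents give no rate of steroid-requiring grade 2 pneumonitis. Purely as an assumption, let that rate p lie between 0.5% and 3%. With the maximum accrual of 40 (13.2.1), the expected number of such patients is 40p: 40 × 0.005 = 0.2 up to 40 × 0.03 = 1.2. These are patients in whom the question would arise, not patients wrongly re-dosed. Going further needs the share who would be restarted despite 6.2, for which the documents offer no basis, so no figure is given.

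**The case against.** The strongest reply is that both sections can be obeyed at once. 5.5.2 sets minimum conditions before retreatment is considered and never requires re-dosing; 6.2 removes certain patients first. The headings show a hierarchy, with 6.1 general and 6.2 specific, and 5.1 and 5.3 refer to section 6. The pneumonitis sentence is worded as a caution. It would still have work to do if 6.2 governed: for patients who prove not to need steroids, and for patients on steroids for another event who also have grade 1 pneumonitis. The 6.1 cell is garbled in the extracted text and is weak evidence taken alone.

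Most of this stands. A reader might infer that 5.5.2 instructs sites to re-dose patients whom 6.2 stops. The documents do not support that, because a precondition is not an order. A reader might also infer that all neurologic events are in conflict. They are not: CNS events stop under both sections, and the 6.2 footnote removes most of the other serious diagnoses.

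What survives is that a section devoted to restarting after steroids covers all grade 2 events, names pneumonitis, and carries neither an exception nor a pointer to the rows that stop. The reader has to supply the precedence.

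**Conclusion.** The inconsistency is real and minor. It is clearest for grade 2 pneumonitis, which 5.5.2 names, and narrow for neurologic events. 6.2 is the likelier intended rule, and harm would require a site to overlook an explicit table row. Even then, 5.5.2 imposes 2 weeks off steroids and Grade 0 or baseline for pneumonitis. It protects less for non-CNS neurologic events, where Grade 1 or lower is enough.

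No reliable magnitude can be derived from the documents; the judgment that few patients are affected rests on the small trial and the assumed range above. A reader might infer that the trial's result is exposed. It is not: the primary endpoint is confirmed response among all eligible, consented patients who began treatment, so stopping or restarting nivolumab does not change who is counted, and the 35-patient design and its error rates stand.

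**What to change.** 1. Add an exception to 5.5.2, and cross-reference it from the grade 2 immunologic row of 6.1: *except grade 2 pneumonitis or grade 2 neurologic events requiring steroids, and the diagnoses in the 6.2 neurologic footnote, for which nivolumab is permanently discontinued per 6.2.*
2. Qualify the mention of pneumonitis in the 5.5.2 retreatment sentence to match.
3. Keep the allowance in 5.5.2 and 6.3 for patients found not to need steroids, and the grade 3 thyroiditis and skin rash exceptions.
4. Have the sponsor confirm whether isolated nerve VII palsy treated with steroids may resume. The 6.2 row leaves this open, and the amendment should not settle it by accident.

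Do not add a general sentence that 6.2 prevails wherever one of its rows stops nivolumab. The grade 3 endocrine row in 6.2 ends study treatment, so such a sentence could cancel the grade 3 thyroiditis exception in 5.5.1 and 5.5.2.

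The cost is amendment wording, with no change to visits, sample size or analysis. The downside is that a few patients who might have been retreated under 5.5.2 are stopped, as 6.2 already says.

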Patients being tapered after high dose corticosteroids over one month followed by a two-week observation period will be allowed an additional two weeks to restart treatment (a maximum eight week interruption). Dosing interruptions > 6 weeks that occur for non-drug-related reasons may be allowed if approved by the Investigator. Prior to re-initiating treatment in a subject with a dosing interruption lasting > 6 weeks, the Principal Investigator must be consulted.
- h) The following exceptions do NOT require permanent study discontinuation:
 - Any other grade 3 non-skin, drug-related AE (other than grade 3 immune mediated event) lasting < 7 days including fatigue.
 - Any grade 3 or 4 drug-related laboratory abnormality or electrolyte abnormality, not associated with underlying organ pathology, that does not require treatment except for electrolyte replacements **does not** require treatment discontinuation.
 - Grade 3 or 4 amylase or lipase abnormalities that are not associated with diabetes mellitus (DM), associated liver or gall bladder inflammation clinical manifestations of pancreatitis and which decrease to 0 Grade 0 **may** resume study treatment when resolved.

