5.5 Criteria to Resume Treatment

5.5.1 General Criteria for Restarting Nivolumab:

Some patients may continue to benefit from treatment, maintaining or improving responses after progression including those treated with steroids.

Restarting applies only to grade 2 events and some grade 3 events (skin rash and thyroiditis). The section should emphasize stopping treatment and starting steroids earlier to obtain resolution with the possibility for restarting rather than waiting for higher grade events.

For non-autoimmune or non-inflammatory events patients may resume treatment with study drug when the drug-related AE(s) resolve to Grade ≤ 1 or baseline value, with the following exceptions:

- Patients may resume treatment in the presence of Grade 2 fatigue
- Evaluation to exclude any additional immune mediated events endocrine, GI, and liver / pancreas function as clinically indicated must be made prior to restarting.
- Non-drug-related toxicity including hepatic, pulmonary toxicity, diarrhea, or colitis, must have resolved to baseline before treatment is resumed.

If the criteria to resume treatment are met, the patient should restart treatment no sooner than the next scheduled time point per protocol. However, if the treatment is delayed past the next scheduled time point per protocol the treatment should resume at the earliest convenient point that is within the six week delay period.

If treatment is delayed for > 6 weeks, (> 8 weeks for patients on a steroid taper), the patient must be permanently discontinued from study therapy, except as specified in Section 5.3 (Duration of Therapy).

It should be emphasized that if adverse event occurs which requires treatment with steroids, it is preferable to withhold nivolumab and start steroids earlier to obtain resolution with the possibility for restarting nivolumab, rather than just waiting for higher grade events.

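### The endocrine note in 6.2 draws the permanent-stop boundary for hypophysitis more narrowly than 5.5.2 and the neurologic footnote, so a site using that table alone could resume a patient the protocol stops

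*Combined protocol and SAP*

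**What the plan says.** Three current places in the protocol bear on when hypophysitis ends treatment.

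- **Section 6.2, note to the endocrine table.** Grade 3 applies to patients with "symptomatic pituitary enlargement, exclusive of hormone deficiency, but including severe headache or enlarged pituitary on MRI should be considered grade 3 events". The note then sets simple deficiency apart: "Isolated thyroid or testosterone deficiency may be treated as grade 2 if there are no other associated deficiencies and adrenal function is monitored".
- **Section 5.5.2.** To be treated as grade 3: "hypophysitis with symptoms of headache, visual or neurologic changes or radiologic evidence of pituitary enlargement and other CNS events such as aseptic meningitis or encephalitis". Headache carries no severity limit here.
- **Section 6.2, footnote to the neurologic table.** It begins "Patients with any CNS events including aseptic meningitis, encephalitis, symptomatic hypophysitis" and, after listing further conditions, takes these patients off study. Again there is no severity limit.

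The grade decides what happens next. In the endocrine table, grade 2 is held until hormone replacement is stable, with the added condition "If treated with steroids patients must be stable off steroids for two weeks. Resume at same dose level". Grade 3 in the same table ends study treatment. Section 5.5.1 allows restart for grade 2 events and, among grade 3 events, only for skin rash and thyroiditis. Section 6.1 takes grade 3 immunologic events off therapy subject to the exceptions in 5.3, and the general grade 3 exception in 5.3 item h leaves out immune-mediated events.

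**The concern.** A site managing hypophysitis would naturally open the table that carries its name. That table's note has the narrowest stop definition of the three and refers to neither 5.5.2 nor the neurologic footnote. The fuller definition sits under a heading about restarting after corticosteroids.

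At stake is re-exposure to nivolumab of a patient whom 5.5.2 would stop for good. Section 5.5.2 shows the protocol's caution here: it treats new or worsening immune events during steroid treatment or taper as a reason for permanent discontinuation. Hypophysitis is also foreseeable. The risk list in 7.1 places it among the less likely events (up to 20%), not the rare ones, and 13.4.1 names endocrinopathy among the events to be followed over time.

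**Working it through.** No arithmetic beyond a count applies, and the plan states no figure to reproduce. The check sets the definitions side by side.

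**Step 1: triggers.** Section 5.5.2 names four.

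| Trigger in 5.5.2 | Endocrine note in 6.2 | Result |
|---|---|---|
| Enlargement on imaging | Enlarged pituitary on MRI | Same sense |
| Headache, any severity | Headache only if *severe* | Narrowed |
| Visual changes | Not named on their own | Missing unless enlargement is present |
| Neurologic changes | Not named on their own | Missing unless enlargement is present |

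Count: 1 matched + 1 narrowed + 2 not named = 4. This compares wording; it is not a rate.

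**Step 2: cases.** Take a patient with hypophysitis.

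| Presentation | 5.5.2 | Endocrine note read alone |
|---|---|---|
| Enlarged pituitary on MRI, with or without symptoms | Grade 3, stop | Grade 3, stop |
| Severe headache | Grade 3, stop | Grade 3, stop |
| Mild or moderate headache, no enlargement | Grade 3, stop | Not captured; could be graded 2 and resumed |
| Visual or neurologic change, no enlargement | Grade 3, stop | Not named; could be graded 2 and resumed |
| Hormone deficiency only, stable on replacement | May restart | Set apart from grade 3 |

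The third and fourth rows differ. The last row shows no conflict.

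**Step 3: does another rule close the gap?** Section 6.1 and section 5.5.2 both require a grade 2 event to settle before retreatment. That delays resumption but does not prevent it. A moderate headache that resolves would let a patient graded 2 resume, whereas 5.5.2 grades the same patient 3 and 5.5.1 then bars restart. Section 5.3 item c discontinues for grade 2 blurred vision that needs systemic treatment, or that fails topical therapy and does not improve. This covers only part of the visual row. The neurologic footnote does reach both differing rows, but from a different table, and it does not define *symptomatic*.

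**Step 4: which text is the outlier?** Section 5.5.2 and the neurologic footnote agree in setting no severity limit on symptoms. The endocrine note stands apart.

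**The case against.** The strongest reply is that the endocrine note does not set an exhaustive boundary. It uses the word *including*, and it nowhere says that hypophysitis with a milder headache is grade 2 or may resume. All three texts can be applied together, and the stricter one then governs. The neurologic footnote is in the same section, in the table just before the endocrine one, and hypophysitis with headache or visual change is symptomatic on any ordinary reading. The neurologic table also takes most cranial neuropathies off study, and grade 2 neurologic events that need steroids off therapy. A site deciding on restart should be reading 5.5 anyway. Section 6 directs sites to the Appendix C algorithms, which may settle the matter.

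Much of this stands. A reader might infer that 6.2 as a whole permits these patients to resume; it does not, because its own neurologic footnote stops them. Nor does the note expressly permit resumption. Symptoms with enlargement are already covered.

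Two things remain. The qualifier *severe* has no function if any headache qualifies, so the natural reading leaves milder headache out. And the route to error needs only a site that doses from the one table whose title names the condition. On Appendix C, the missing flowcharts are a limit of this copy and do not count against the plan. Whatever they say, the body text still carries two different definitions.

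**Conclusion.** The point holds as a minor safety inconsistency in wording. It is confined to hypophysitis with a non-severe headache, or with visual or neurologic change, and no enlargement on MRI. It matters only if a site works from the endocrine table alone. No frequency can be derived from the documents.

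Three stronger inferences are not supported:

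- **That deficiency-only patients face contradictory rules.** The endocrine note and the hypopituitarism sentence in 5.5.2 both set deficiency apart.
- **That the statistical design is affected.** The response-rate decision rules in 13.1.4 and the power and significance level in 13.1.5 do not use this grade. The adverse event stopping rule in 13.5.2 counts only grade 4 and grade 5 events.
- **That the protocol has no stop rule for these patients.** Section 5.5.2 and the neurologic footnote both supply one.

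The conclusion rests on the text visible here. The Appendix C endocrine and neurologic flowcharts could not be checked.

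**What to change.** Replace the first sentence of the endocrine note. The new sentence should class as grade 3 any hypophysitis with headache of whatever severity, visual change, neurologic change, or enlargement on imaging. It should keep hormone deficiency alone outside the definition and refer the reader to 5.5.2 and the neurologic footnote. The deficiency carve-out must stay in the endocrine note itself; a reader of that table could miss it elsewhere.

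Leave the sentence on isolated thyroid or testosterone deficiency and the hypopituitarism restart rule in 5.5.2 as they are. Confirm that the Appendix C endocrine and neurologic algorithms use the same boundary.

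The cost is one sentence, two cross-references and a check of two flowcharts. It needs no extra patients, visits or data. The downside is that a few patients with hypophysitis and a milder headache will be stopped under the endocrine table, which 5.5.2 already requires.
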